4.5.1.3 Dose modification for toxic range rapamycin level

If the rapamycin level at the time of scheduled measurement is >15 ng/mL, the dose will be held for 5 days, and a repeat level will be drawn on the 5^{th} day. If the level is still >15, the drug will be held for 5 more days and the level repeated. Once the repeat level is no longer above the normal range, the daily dose will be reduced to 1 mg and a rapamycin level will be drawn 5 days after the dose adjustment has been made. If the level is again ≥ 15 ng/dL, drug will be held until levels return to the therapeutic range and then started again at 1 mg every other day.

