4.1.1 Study schema

Note: Those patients with morphologic M4/M5 subtypes²⁸ will be treated on Arm B and all other subtypes on Arm A. At study entry, all patients will have samples procured for testing of eIF4E expression but this will not determine allocation to arm A or B which will be made solely on the basis of FAB subtype. M4 subtype is acute myelomonocytic leukemia and M5 acute monocytic leukemia.

- Decitabine (Arms A and B)
- 20mg/m2 will be given as an intravenous infusion daily for 10 consecutive days starting on day 1 of cycle 1.
- In subsequent cycles, decitabine will be given for 5 days (day 1-5)

Rapamycin (Arm A)

- o For non-M4/M5 AML cases²⁸
- A 6 mg loading dose will be administered on Day 11 in cycle 1 and day 6 in subsequent cycles. Thereafter, 2 mg/day will be administered per schedule below. This may be reduced to 1 mg/day if levels are elevated (>15 ng/mL).
- o Toxicities will be as defined in section 9 using NCI Common Toxicity Criteria for Adverse Events (CTCAE (version 4.0) Appendix 3)
- o Rapamycin will be given from day 11 to 22 in cycle 1 and on days 6 to 22 in subsequent cycles.

Dose Level	Rapamycin	Decitabine
Level -1	1 mg	20 mg/m2
Level 1	2 mg	20 mg/m2

The rapamycin dose for phase II of the study was chosen based on results from the phase I study (ULEU08049).

Ribavirin (Arm B)

For M4/M5 cases²⁸—These patient are anticipated to have high eIF4E expression as expressed by Western blotting²⁴.

In cycle 1, ribavirin will be dosed from Day 11 through Day 28.

In subsequent cycles, ribavirin will be started on Day 1 on a continuous basis until study completion. These doses were chosen based on those found effective and tolerated in previous studies²⁴.

Dose level cohorts are listed in the table below. Subject enrollment will start at **Dose Level 1** (1000 mg). Enrollment in subsequent dose levels (escalation to Dose level 2 and 3, or de-escalation to Level -1 and -2) will follow the dose escalation and dose de-escalation plans as outlined below.

ULEU-13049 14 Version date: 09Aug2017

Dose Level	Ribavirin	Decitabine	Description
Level -2	600 mg bid	20mg/m2	Dose de-escalation cohort
Level -1	800 mg bid	20mg/m2	Dose de-escalation cohort
Level 1	1000 mg bid	20mg/m2	Initial cohort
Level 2	1200 mg bid	20 mg/m2	Dose escalation cohort
Level 3	1400 mg bid	20mg/m2	Dose escalation cohort

Dose Escalation Plans for Ribavirin (Arm B)

Number of patients with DLT at a given dose level	Escalation Decision Rule

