5.2 Rapamycin (from Rapamycin package insert)

Rapamycin can be obtained as Rapamune® from Wyeth-Ayerst Laboratories. It is approved for graft rejection prevention in kidney transplantation. It will be purchased from commercial sources for this protocol.

The oral solution must be protected from light and stored under refrigeration, 2 degrees Celsius to 8 degrees Celsius and it is stable for 24 months under these conditions. A slight haze may develop in refrigerated solutions, but the quality of the product is not affected. After opening, the solution should be used in 1 month. If necessary, it may be stored at temperatures up to 25 degrees Celsius for several days after opening (not longer than 30 days). Product may be stored in an amber syringe for a maximum of 24 hours (at room temperature or refrigerated). Discard syringe after use. Solution should be used immediately following dilution. The tablet should be stored at room temperature (20 degrees Celsius to 25 degrees Celsius) and protected from light.

Absorption: Rapid

Volume of distribution: 12L/Kg (+/- 7.52L/kg) Protein binding: 92%, primarily to albumin

Metabolism: Extensively hepatic via CYP3A3/4 and P-glycoprotien

Bioavailability: 14%

Half-life elimination: Mean: 62 hours

Time to peak: 1 - 3 hours

Excretion: Feces (91%); Urine (2.2%)

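### Section 4.5.1.3 prints the second rapamycin hold limit as 15 ng/dL, 100-fold below the 15 ng/mL limit used in the rest of the rule

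*Combined protocol and SAP*

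**What the plan says.** The rule for high rapamycin levels in section 4.5.1.3 is a sequence of steps, each with its own condition:

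- **Initial hold:** "If the rapamycin level at the time of scheduled measurement is >15 ng/mL, the dose will be held for 5 days".
- **Repeat level, on the fifth day:** "If the level is still >15, the drug will be held for 5 more days and the level repeated". No unit is printed here.
- **Restart:** "Once the repeat level is no longer above the normal range", the dose drops to 1 mg daily, and a new level is drawn 5 days after that change.
- **Second hold:** "If the level is again ≥ 15 ng/dL", in which case "drug will be held until levels return to the therapeutic range" and rapamycin restarts at 1 mg every other day.

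Section 4.1.1 states the limit separately when it describes Arm A dosing: "This may be reduced to 1 mg/day if levels are elevated (>15 ng/mL").

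**The concern.** One paragraph uses the number 15 three times for what is evidently one limit: once in ng/mL, once with no unit and once in ng/dL. The ng/dL version belongs to an operative instruction. It decides whether a patient whose dose has already been reduced is stopped again and dropped to the lowest dose in this rule.

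Two things are at stake. A site that follows the text exactly would halve the average dose (1 mg daily to 1 mg every other day) in patients whose level no longer calls for it. A site that applies the sensible limit would depart from the written rule. Staff and monitors should not have to choose between the two.

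**Working it through.** **Inputs**

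- Initial hold limit: >15 ng/mL (4.5.1.3), the same as the elevated-level limit in 4.1.1.
- Second hold limit as printed: ≥15 ng/dL (4.5.1.3).
- "Half-life elimination: Mean: 62 hours" (5.2).
- Interval from the high level to the recheck: a 5-day hold, then a level 5 days after the dose change, so about 10 days. It is 9 to 11 days depending on whether the first held dose is on the day of the draw or the next day, and on whether dosing resumes on the day of the repeat level or the next day.

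**Step 1: unit conversion.** 1 dL = 100 mL, so 15 ng/dL = 15 / 100 = 0.15 ng/mL. The ratio of the two printed limits is 15 / 0.15 = 100. In the other direction, 15 ng/mL is 1,500 ng/dL. This step alone establishes the contradiction.

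**Step 2: what the literal limit would do.** Assume first-order elimination, a level of exactly 15 ng/mL at the initial check, one hold and no doses afterwards. The level after *t* hours with half-life *h* is 15 × 2^(−t/h).

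| Interval | Half-life | Level (ng/mL) | Multiple of 0.15 |
|---|---|---|---|
| 9 days (216 h) | 62 h | 15 × 2^(−216/62) = 1.34 | 8.9 |
| 11 days (264 h) | 62 h | 15 × 2^(−264/62) = 0.78 | 5.2 |
| 11 days (264 h) | 50 h (assumed) | 15 × 2^(−264/50) = 0.39 | 2.6 |
| 11 days (264 h) | 80 h (assumed) | 15 × 2^(−264/80) = 1.52 | 10.1 |

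For the level to fall to 0.15 ng/mL with no dosing, it must drop 100-fold. The half-life would then have to be no more than 264 / log2(100) = 39.7 h over 11 days, or 216 / log2(100) = 32.5 h over 9 days.

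The assumptions about level and dosing are conservative: the triggering level is above 15, and 1 mg doses are to be given before the recheck. Both raise the level at the recheck.

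**Step 3: internal logic.** A patient reaches the second-hold step only after a repeat level that is no longer above the normal range. Under the printed limit, that patient would then be held until the level came back to a range it need not have left. The step makes sense only if its limit is the one that triggered the initial hold.

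**Step 4: the inequality.** The change from > to ≥ matters only for a level of exactly 15. It is an inconsistency, but has almost no effect of its own.

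**The case against.** The strongest reply is that this is a slip that the paragraph itself corrects. The section is headed as dealing with toxic-range levels, it opens at 15 ng/mL, and a level cannot *again* reach a limit that was never set before. A clinician would read 15 ng/mL. Even on the literal reading, an in-range patient already meets the condition for ending the hold. The consequence is a lower dose in someone who has already run high, not over-exposure. The documents do not say how many patients exceed 15 ng/mL at all.

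Most of this stands, and it limits the weight of the point. It does not remove it: even if the hold itself were empty, the restart at 1 mg every other day would still follow.

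Three stronger readings are tempting, and the documents do not support them.

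- **That the half-life figures are a floor for every patient.** Section 5.2 gives only a mean half-life. The 62-hour results are values at that mean, and a patient who clears the drug faster would be lower.
- **That 15 ng/mL is also the top of the normal and therapeutic ranges, so that every step could be rewritten around it.** No section gives a figure for either range. If either ends below 15 ng/mL, that edit would loosen the restart condition.
- **That the rule breaks down because dosing stops on day 22 ("Rapamycin will be given from day 11 to 22 in cycle 1 and on days 6 to 22 in subsequent cycles"), so the recheck needs a new time point.** The reductions in 4.1.1 and 4.5.1.3 carry no cycle limit, so the natural reading is that the reduced dose continues. Section 4.5.4 leaves other modifications to the physician. Moving the recheck to the next cycle's day 14 trough could delay a level that the protocol wants at 5 days.

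**Conclusion.** Wrong as written. The limit for the second rapamycin hold is printed 100-fold too low, in conflict with the opening of the same paragraph and with section 4.1.1. This rests on the unit conversion alone and needs no assumption.

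That the literal rule would catch nearly every patient who reaches the step rests on more: first-order elimination, a half-life near the stated mean, and the 9 to 11 day interval after a single hold. It holds over the assumed half-lives of 50 to 80 hours.

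The intended value can be inferred, so the likely practical effect is small. The error touches only Arm A patients who have already had a hold and a reduction. It should be corrected because it sits in a mandatory dosing instruction, not because it threatens the trial's conclusions. Sample size, alpha and power do not depend on it.

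**What to change.** Make two edits in section 4.5.1.3:

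1. In the second-hold step, change "If the level is again ≥ 15 ng/dL" so that the condition is a level that is again >15 ng/mL.
2. In the intermediate check, add the unit so that the condition is a level still >15 ng/mL.

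Leave the references to the normal and therapeutic ranges, and the level drawn 5 days after the dose change, as they stand.

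The cost is a wording correction to one paragraph. It adds no visits or blood draws and has no statistical consequence.

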4.5.2 Decitabine

No specific dose modification for hematologic toxicities.

Schedule modifications will be based on disease status and count recovery from the previous cycle as follows:

Subjects with >5% blasts in marrow will proceed to a 5 day cycle.

Those with no morphological evidence of leukemia (<5% blasts)will receive a 5 day course of decitabine

Those with no evidence of AML but who have grade 4 neutropenia (<500/uL) of at least 14 days duration will receive 5 days with the next cycle. If this happens again in the subsequent cycle, 3 days will be administrated.

Subjects should receive 3 cycles of treatment as discussed above before treatment failure is determined in the absence of obviously resistant, progressive disease.

4.5.3 Ribavirin

4.5.3.1 Dose Modifications for Hematologic Toxicity

No dose modification for hematologic toxicity will occur. Patients will receive supportive care as specified in section 4.2. Cycles may be delayed up to a week in the event of stable disease if severe neutropenia and/or active infection are present until the infection is controlled and neutropenia stabilizes or is improving.

4.5.3.2 Dose Modifications for non-hematologic toxicity

For non-hematologic toxicities thought due to ribavirin, the drug will be held until toxicity resolves to less than or equal to grade 1. If the resumption of ribavirin results in the same toxicity, dose will be lowered by one cohort, and for those on 1000 bid, dose may be reduced to 800 mg bid (dose level -1). If toxicity occurs at that level, ribavirin will be redosed at 600 mg bid (dose level -2), and if toxicity occurs at that dose, ribavirin will be stopped.

ULEU-13049 20 Version date: 09Aug2017

Grade 3 infections, fatigue, weight loss, and electrolyte imbalances are anticipated in relapsed AML patients and will be appropriately treated but are not deemed study related toxicities and will not result in dose modifications

4.5.4 Other dose modifications according to standard clinical practices are to the discretion of the treating physician. The study coordinator and primary investigator (s) should be notified of such modifications. As examples, treatment can be delayed at the discretion of the investigator for disease-related complications such as febrile neutropenia, infection, mucositis, hemorrhage, or extreme fatigue and debility.

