5.1.1.3 Other Pertinent Information

In stability studies, ³³ Dacogen for Injection maintains at least 95% of its initial potency for up to 60 minutes when a 50 mg vial is reconstituted

with 10 mL of either cold (2°C to 8°C) or room temperature water for injection (WFI). To assess potency, the decitabine was assayed by high-performance liquid chromatography (HPLC).

Reconstituted Dacogen for Injection (5mg/mL in WFI) was mixed with each of the approved diluents (0.9% sodium chloride injection, 5% dextrose injection or lactated Ringer's solution) and the stability was measured as above. The decitabine potency at diluted concentrations of 0.1 mg/mL and 1.0 mg/mL at either room temperature for 3 hours or refrigerated (2°C to 8°C) for 7 hours followed by 2 hours at room temperature remained \geq 90%. All admixtures of decitabine remained clear and colorless during storage at room temperature. Additionally, the pH of the solutions remained constant throughout the study.

Handling and Disposal

Procedures for proper handling and disposal of anticancer drugs should be applied. Several guidances on this subject have been published. There is no general agreement that all of the procedures recommended in the guidelines are necessary or appropriate.

5.1.1.4 The dosage of decitabine will be 20 mg/m2 given as an infusion on Days 1-10 of the first cycle and 1-5 of subsequent cycles.. Decitabine must be infused over 1 hour.

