5.2.2. Drug Interactions

Cyclosporine may increase rapamycin concentrations due to inhibition of CYP3A4. In this protocol, active GVHD is an exclusion (see inclusion/exclusion section), so it is unlikely any patient would be on concurrent cyclosporine.

It is recommended that strong inducers and strong inhibitors of CYP3A4 and P-gp be avoided with rapamycin. Such agents include but are not limited to Rifampin, Rirabutin, Ketoconazole, Voriconazole, Itraconazole, Erythromycin, Telithromycin, and Clarithromycin.

Note: None of these are commonly used in AML patients except voriconazole, and it is recommended to avoid this. (See supportive care section of protocol, section 4.2). If any of these agents or other weaker inducers of CYP3A4 require usage, these can be utilized with caution especially since rapamycin levels will be monitored frequently in this protocol.

Grapefruit juice is to be avoided with rapamycin use.

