5.3.3 Adverse Effects

6.3.3.1 Ribavirin therapy should not be started unless a report of a negative pregnancy test has been obtained immediately prior to planned initiation of therapy. Extreme care must be taken to avoid pregnancy in female patients and in female partners of male patients. Patients should be instructed to use at least two forms of effective contraception during treatment and for 6 months after treatment has been stopped. Pregnancy testing should occur monthly during therapy and for 6 months after therapy has stopped.

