5.3.3.2 Anemia

The primary toxicity of ribavirin is hemolytic anemia, which was observed in approximately 13% of all ribavirin/interferon-treated subjects in clinical trials. Anemia occurs within 1 to 2 weeks of initiation of therapy. Because the initial drop in hemoglobin may be significant, it is advised that hemoglobin or hematocrit be obtained pretreatment and at week 2 and week 4 of therapy or more frequently if clinically indicated. This has not been a factor in AML trials thus far. ²⁴

5.3.3.3 Hepatic Failure –this has been noted only in hepatitis C patients.

5.3.3.4 Other reported toxicities:

Pruritis

Severe acute hypersensitivity reactions.

Low calcium levels

Low magnesium levels

Serious skin reactions including vesiculobullous eruptions, reactions in the spectrum of Stevens-Johnson Syndrome (erythema multiforme major) with varying degrees of skin and mucosal involvement and exfoliative dermatitis (erythroderma) have been reported in patients receiving PEGASYS with and without ribavirin. Patients developing signs or symptoms of severe skin reactions must discontinue therapy.

Pulmonary Disorders

Dyspnea, pulmonary infiltrates, pneumonitis, pulmonary hypertension, and pneumonia have been reported during therapy with ribavirin and interferon.

Bone Marrow Suppression

Pancytopenia (marked decreases in RBCs, neutrophils and platelets) and bone marrow suppression have been reported in the literature to occur within 3 to 7 weeks after the concomitant administration of pegylated interferon/ribavirin and azathioprine. This has been reversible and is of less concern in patients with hematologic malignancies.

Pancreatitis

Ribavirin therapy should be suspended in patients with signs and symptoms of pancreatitis, and discontinued in patients with confirmed pancreatitis.

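### The general ribavirin hold, resume and reduce rule (4.5.3.2) has no exception for severe skin reactions and confirmed pancreatitis, for which 5.3.3.4 requires discontinuation

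*Combined protocol and SAP*

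**What the plan says.** Section 4.5.3.2 sets the dosing rule for ribavirin in Arm B. Its first step is: "For non-hematologic toxicities thought due to ribavirin, the drug will be held until toxicity resolves to less than or equal to grade 1". Its second is: "If the resumption of ribavirin results in the same toxicity, dose will be lowered by one cohort". A patient on 1000 mg bid may go down to 800 mg bid, and after toxicity there is redosed at 600 mg bid. The only stopping condition comes at that last level: "if toxicity occurs at that dose, ribavirin will be stopped". The only exclusions are grade 3 infections, fatigue, weight loss and electrolyte imbalances.

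Section 5.3.3.4 lists other toxicities reported with ribavirin. After describing serious skin reactions, including those in the Stevens-Johnson spectrum, it says: "Patients developing signs or symptoms of severe skin reactions must discontinue therapy". On pancreatitis it says: "Ribavirin therapy should be suspended in patients with signs and symptoms of pancreatitis, and discontinued in patients with confirmed pancreatitis".

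**The concern.** A severe skin reaction and confirmed pancreatitis are both non-hematologic, and neither is among the exclusions in 4.5.3.2. When either is attributed to ribavirin, both sections apply. The dosing rule leads to a hold with possible resumption and stepwise reduction; the toxicity section calls for discontinuation.

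The stake is the safety of individual Arm B patients. Staff who dose from 4.5.3.2 alone could restart ribavirin after a Stevens-Johnson-type reaction or after confirmed pancreatitis. That section would permit it, and nothing in it sends them to the place where the protocol says to stop.

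**Working it through.** No statistical figure is involved, so the check compares the texts and counts the steps of the dosing rule.

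**1. The two sections, event by event (event attributed to ribavirin)**

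| Event | 4.5.3.2 | 5.3.3.4 | Compatible as written? |
|---|---|---|---|
| Signs or symptoms of a severe skin reaction | Hold to grade 1 or less; reduce if it recurs on resumption | Discontinue | Only if ribavirin is not resumed |
| Suspected pancreatitis | Same | Suspend | Yes, at the hold step |
| Confirmed pancreatitis | Same | Discontinue | Only if ribavirin is not resumed |

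The inconsistency is therefore limited to the first and third rows.

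**2. Is section 5 only background?**

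Section 5.3 is labelled as taken from the package insert, but section 5 also carries instructions that sites are plainly meant to follow. Section 5.3.3 says: "Ribavirin therapy should not be started unless a report of a negative pregnancy test has been obtained". Section 5.1.1.4 says: "Decitabine must be infused over 1 hour". The second comes from the decitabine part, which has no package-insert label, so the pregnancy-test instruction is the better support. The discontinuation sentences can fairly be read as instructions too.

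**3. Does any other text settle which section governs?**

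- Section 4.1 says that adverse events and risks are described in section 5. It sets no precedence.
- Section 4.5.4 leaves other modifications to the physician's discretion. It requires no stop.
- Section 9.4 defines a DLT. It does not say that a patient who has one stops ribavirin.
- Section 15.0 allows discontinuation from study for unacceptable toxicity. It is permissive and names no event.
- The Arm B calendar in Appendix 5 has ribavirin given continuously after cycle 1 unless toxicity interrupts it. It adds no stopping rule.

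None of these reconciles the two sections. The protocol does cross-refer elsewhere: section 5.2.2, on rapamycin interactions, tells the reader "See supportive care section of protocol, section 4.2".

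**4. Re-exposures that 4.5.3.2, read alone, permits from 1000 mg bid**

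- Toxicity does not resolve to grade 1 or less, or the physician does not resume: 0.
- Resumed, by implication at 1000 mg bid, with no recurrence: 1.
- Recurs, then given at 800 mg bid: 1 + 1 = 2.
- Toxicity at 800 mg bid, then given at 600 mg bid: 2 + 1 = 3.
- Toxicity at 600 mg bid: stop.

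The range is 0 to 3. Under 5.3.3.4, reading discontinued as not resumed, the count is 0 for both events. No count is given for 1200 or 1400 mg bid, because the full sequence is spelled out only from 1000 mg bid.

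**The case against.** The strongest reply is that the two sections do not contradict each other. Section 4.5.3.2 is a general rule and 5.3.3.4 gives specific instructions for named events. Resumption is worded conditionally, so a site that follows 5.3.3.4 complies with both. The stop instruction is already in the protocol, and section 4.1, at the head of the treatment plan, refers to section 5 for ribavirin risks. Physician discretion, 24-hour telephone reporting of fatal or life-threatening events (9.3) and safety review between cohorts make repeated, unnoticed rechallenge unlikely. The skin sentence also needs interpretation, since it concerns reactions in patients receiving a peginterferon product with or without ribavirin.

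Much of this stands, and it limits the point to low-to-moderate importance. It does not remove it. That the specific instruction overrides the general rule is a sensible reading, but the protocol does not state it. The later steps of 4.5.3.2 are also firmer than the first: after recurrence the dose is to be lowered, and after toxicity at 800 mg bid the drug is to be given again at 600 mg bid. Applied to these two events, those steps prescribe what 5.3.3.4 rules out. The reporting and review provisions do not require a stop. The pancreatitis sentence names ribavirin and needs no interpretation on that score.

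A reader might infer that the protocol compels rechallenge or lacks a stop rule for these events. The documents support neither: the first resumption is not ordered, and the stop rule is in 5.3.3.4. A reader might also treat the absence of grade tiers, which the rapamycin rule in 4.5.1.1 has, as evidence of the conflict. It is not; a single-tier rule is a design choice and would be consistent with 5.3.3.4 if it carried the exception.

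**Conclusion.** The point holds for two events only. The general ribavirin rule omits an exception that 5.3.3.4 requires for severe skin reactions and confirmed pancreatitis. It should be fixed, as a safety inconsistency of low to moderate weight. Suspected pancreatitis is not in conflict.

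The conclusion rests on two readings: that therapy in the skin-reaction sentence means ribavirin, since the sentence stands in the ribavirin section, and that discontinued means not resumed, since 5.3.3.4 does not mention rechallenge.

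The figure of 0 to 3 re-exposures lists the branches of 4.5.3.2 read in isolation. It is not a forecast: the upper end needs the reaction to resolve to grade 1 or less and ribavirin to be restarted three times despite 5.3.3.4. The documents give no incidence for these reactions in this population.

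A reader might infer that dose finding is compromised as well. The documents do not support that. The DLT definition turns on grade, type and attribution, and the escalation rules count patients with a DLT; neither depends on whether ribavirin is later resumed in the affected patient. The Arm A analysis does not involve ribavirin.

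**What to change.** Add one sentence to 4.5.3.2:

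> *Exception: ribavirin is permanently discontinued for severe skin reactions or confirmed pancreatitis, and suspended for signs or symptoms of pancreatitis until it is confirmed or excluded (see 5.3.3.4).*

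Add a reference back to 4.5.3.2 in 5.3.3.4. The word permanently is proposed here; it makes explicit what 5.3.3.4 leaves to be understood.

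The cost is a short written amendment, with review board approval under section 14.0 if it is classed as significantly affecting safety, and a note to staff. It adds no visits, procedures or patients.
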